7.7.2 Safety and Tolerability Variables

The following are defined as safety/tolerability variables:

- Injection site reactions
- Physical examination
- Adverse events
- Clinical laboratory assessments including hematology, serum biochemistry, and urinalysis
- Vital Signs
- 12-lead ECG
- 3-lead ECG (telemetry)
- Immune reactions
- Concomitant medications/therapy

The safety set will be used for analyses.

7.7.3 Analysis of Safety and Tolerability Endpoints

7.7.3.1 Injection Site Reactions

Injection site reactions consisting of dryness, redness, swelling, pain/tenderness and itching assessed by the Investigator will be summarized by tabulating the number and percentages for each time point. For evaluations: severity (none, mild, moderate, severe) and clinical significance (Abnormal NCS and Abnormal CS), the count and percentage will be provided.

7.7.3.2 Physical Examination

Results of physical examinations consisting of general appearance, skin/subcutaneous tissue, ears / eyes / nose / throat, head / neck, lungs / chest, cardiovascular system, gastro-intestinal tract (GIT), musculoskeletal (extremities), neurological, and lymphnodes conducted throughout the study will be presented in listings.

7.7.3.3 Adverse Events

An AE is any untoward medical occurrence in a patient or clinical investigation subject administered a pharmaceutical product and which does not necessarily have a causal relationship with this treatment. An AE can therefore be any unfavorable and unintended sign (including an abnormal laboratory finding), symptom, or disease temporally associated with the use of a medicinal (investigational) product, whether or not related to the medicinal (investigational) product.

A treatment-emergent AE (TEAE) is any AE temporally associated with the use of a study drug, whether or not considered related to the study drug. A drug-related TEAE is defined as any TEAE that is assessed by the Investigator as possibly, probably, or definitely related to study drug.

Adverse event data will in addition be coded with the latest version of the MedDRA coding system used during the clinical conduct of the study: this is version 25.1 or higher. The SAS programmer or Data Manager of the study will add the coding (using the MedDRA system and SAS) to the AE descriptions extracted from the database.

The TEAEs are tabulated by system organ class (SOC) and preferred terms (PT) within each SOC according to the MedDRA terminology list. They will be tabulated broken down by treatment groups. TEAEs will be summarized in descending order according to incidence of SOC and PT, using the number and percentage of subjects experiencing a TEAE, as well as the number of events.

The TEAEs will also be tabulated by intensity and by relationship to study drug. If the same TEAE recorded separately in more than two rows due to worsen severity, the severity of the AE to the tables will be the highest one. Summary tables will be accompanied by individual subject listings broken down by treatment groups. The same tabulations and listings will be presented for treatment-emergent serious adverse events (TESAEs).

A SAE is defined by the International Council for Harmonisation (ICH) guidelines as any AE fulfilling at least one of the following criteria:

- Results in death.

- Is life-threatening. Life-threatening refers to an event in which the subject was at risk of death at the time of the event. It does not refer to an event that hypothetically might have caused death if it were more severe.
- Requires subject's hospitalization or prolongation of existing hospitalization.
- Results in persistent or significant disability or incapacity.
- Is a congenital anomaly or birth defect.
- Is medically significant or requires intervention to prevent at least one of the outcomes listed above.

The following calculations and derivations will be used, making the most conservative judgment.

For study day of AE relative to study drug:

- Study day = AE start date minus date of (prior) dose administration + 1 by treatment groups if the AE occurred post dosing.
- Study day = 'Prior' if the AE occurred prior to dosing.
- If start date is unknown, study day will be missing.

For duration of AE:

- Duration = stop date and time of the event minus start date and time of the event.
- If start or stop time unknown, then the duration will be calculated based on stop date and start date only, and +1 day is added.
- If start or stop date is unknown, duration will be missing.
- Will be display as "XXDXXXHXXM".

A general summary of all TEAEs and will be provided. This summary will present the numbers and percentages of subjects according to the following categories:

- Subject with Any TEAE
- Subject with Any TESAE
- Subject with Any Drug-Related TEAE
- Intensity
- Action Taken
- Relationship to Study drug
- Outcome
- Serious AE
- Serious criteria

Other summary tables for AEs will be tabulated:

- Treatment-Emergent Adverse Events
- Treatment-Emergent Adverse Events – MedDRA
- Treatment-Emergent Adverse Events by Intensity – MedDRA
- Treatment-Emergent Adverse Events by Relationship – MedDRA
- Treatment-Emergent Adverse Events – MedDRA (Preferred Term over XX %)
- Treatment-Emergent Serious Adverse Events - MedDRA
- Treatment-Emergent Serious Adverse Events by Intensity - MedDRA
- Treatment-Emergent Serious Adverse Events by Relationship – MedDRA
- Listing of Subjects with Treatment-Emergent Serious Adverse Events

- Listing of Subjects with Treatment-Emergent AEs Leading to Death
- Listing of Subjects with Treatment-Emergent AEs Leading to Premature Discontinuation of Study Drug

A general summary of all TEAEs will be provided according to the following categories (empty categories will also be included) on Table 14.3.1.1.

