9.1.2 Intensity of Adverse Events

The intensity of clinical AEs is graded on a three-point scale: mild, moderate, severe, and reported on specific AE pages of the eCRF.

If the intensity of an AE worsens during study drug administration, the AE will be closed and a new AE with enhanced severity will be generated in the eCRF. If the AE lessens in intensity, no change in the severity is required.

If an AE occurs during a washout or placebo run-in phase and afterwards worsens during the treatment phase, a new AE page must be filled in with the intensity observed during study drug administration.

Mild: Event may be noticeable to subject/patient; does not influence daily activities; usually does not require intervention.

Moderate: Event may make subject/patient uncomfortable; performance of daily activities may be influenced; intervention may be needed.

Severe: Event may cause noticeable discomfort; usually interferes with daily activities; subject/patient may not be able to continue in the study; treatment or intervention is usually needed.

A mild, moderate or severe AE may or may not be serious. These terms are used to describe the intensity of a specific event (as in mild, moderate, or severe myocardial infarction). However, a severe event may be of relatively minor medical significance (such as severe headache) and is not necessarily serious. For example, nausea lasting several hours may be rated as severe, but may not be clinically serious. Fever of 39 °C that is not considered severe may become serious if it prolongs hospital discharge by a day (see Section 9.2.1.2). Seriousness rather than severity serves as a guide for defining regulatory reporting obligations.

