10.4 Safety and Tolerability Parameters

Definitions of the safety and tolerability parameters are described in Section [8.11.2](#).

The safety set is used to perform all safety analyses.

The medical history is coded using the latest version of MedDRA and listed.

All AEs and SAEs are coded using the latest version of MedDRA.

The treatment-emergent AEs are tabulated by system organ class (SOC), and individual preferred terms within each SOC by treatment group. The number and percentage of subjects/patients who experienced AEs coded with the same preferred term and SOC will be summarized by treatment group (in descending order according to the incidence in the investigational study drug group). Adverse events will also be tabulated by severity and by relationship to study drug. Summary tables will be accompanied by individual subject/patient listings broken down by treatment group, including pre-dose events.

SAEs will be listed and summarized similarly to AEs.

Reasons for death will only be listed.

Reasons for premature discontinuation of study drug will be listed and summarized by frequency tables.

ECG variables, vital sign measurements and laboratory measurements will be summarized at each time point using mean, median, standard deviation, min, max, number of available observations, and change from baseline. Individual subject/patient listings of physical examination data, ECG data, vital signs data, physical examination data, immune reactions, injection site reactions, concomitant medication/therapy and laboratory measurements will be provided.

Standard numeric laboratory parameters are presented in the units supplied. If needed, a conversion will be made to standard units.

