14.3.1.2	Treatment-Emergent Adverse Events - MedDRA	Adverse event summary containing the number and percentage of subjects experiencing TEAEs. TEAEs are tabulated by SOC and PT and summarized by treatment groups. The summary will be presented in descending according to SOC and PT.
14.3.1.3	Treatment-Emergent Adverse Events by Intensity - MedDRA	The same tabulation as 14.3.1.2 will be created for TEAEs by intensity.
14.3.1.4	Treatment-Emergent Adverse Events by Relationship - MedDRA	The same tabulation as 14.3.1.2 will be created for TEAEs by relationship to study drug.
14.3.1.5	Treatment-Emergent Adverse Events - MedDRA (Preferred Term over XX %)	Adverse event summary containing the number and percentage of subjects experiencing TEAEs. TEAEs are tabulated by PT and summarized by treatment groups.
14.3.1.6	Treatment-Emergent Serious Adverse Events - MedDRA	The same tabulation as 14.3.1.2 will be created for TESAEs.
14.3.1.7	Treatment-Emergent Serious Adverse Events by Intensity - MedDRA	The same tabulation as 14.3.1.2 will be created for TESAEs by intensity.

14.3.1.8	Treatment-Emergent Serious Adverse Events by Relationship - MedDRA	The same tabulation as 14.3.1.2 will be created for TESAEs by relationship to study drug.
14.3.2.1	Listing of Subjects with Treatment-Emergent Serious Adverse Events	Listing for all TESAE.
14.3.2.2	Listing of Subjects with Treatment-Emergent AEs Leading to Death	Listing for AEs leading to death.
14.3.2.3	Listing of Subjects with Treatment-Emergent AEs Leading to Premature Discontinuation of Study Drug	Listing for AEs leading to premature discontinuation.
14.3.4	Abnormal Laboratory Values for All Subjects	A subject listing of all data outside the (investigators) reference range, containing the variables test, age, sex, date/time, unit, value, reference range, and whether there were clinical implications (NCS/CS).
14.3.5.1- 14.3.5.3	Laboratory Values over Time - Hematology/ Serum Biochemistry/ Urinalysis	Descriptive statistics for values and change from baseline by time point, per treatment groups.
14.3.5.4- 14.3.5.6	Individual Subject Changes (Shift Table) - Hematology/ Serum Biochemistry/ Urinalysis	Shift table for LB data.
14.3.6	Summary of Vital Sign	Descriptive statistics for values and change from baseline by time point, per treatment groups.
14.3.7- 14.3.8	Summary of 12-Lead ECG/ 3-Lead ECG (Telemetry)	Descriptive statistics for values and change from baseline by time point, per treatment groups.

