14.3.9	Summary of Injection Site Reaction	Descriptive statistics by time point, per treatment groups.
14.3.10	Summary of RA Previous and Concomitant Medication by ATC Level	Summary containing the number and percentage of subjects taking RA previous and concomitant medication by ATC Level.

Full details are provided in SAP Mock Table.

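### The SAP's highest-severity rule for worsening adverse events starts at three rows, but a single worsening produces only two

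*SAP*

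**What the plan says.** Protocol section 9.1.2 grades adverse events as mild, moderate or severe and sets the recording convention. When intensity worsens, "the AE will be closed and a new AE with enhanced severity will be generated in the eCRF". Improvement is treated differently: "If the AE lessens in intensity, no change in the severity is required".

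SAP section 7.7.3.3 then says which grade of a worsening event enters the tables. The highest severity is used under the condition "If the same TEAE recorded separately in more than two rows due to worsen severity".

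The intensity results appear in two places:
- The overall summary, Table 14.3.1.1, has intensity among its categories. SAP section 7.7.3.3 says of it: "This summary will present the numbers and percentages of subjects according to the following categories".
- Table 14.3.1.3 is specified in SAP section 10.2 only by reference to another table: "The same tabulation as 14.3.1.2 will be created for TEAEs by intensity".

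SAP section 10.2 leaves further detail to a separate document: "Full details are provided in SAP Mock Table".

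**The concern.** The SAP rule exists to deal with the extra rows that the protocol's convention creates. The ordinary case is one worsening, which gives two rows, and two is not more than two. Read literally, the rule skips that case and applies only after two successive worsenings of the same event.

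Severity of adverse events is part of the primary endpoint (protocol section 8.1.1), and this is the only stated rule for which grade of a worsening event is tabulated. A programmer who follows it literally has no instruction to drop the lower-grade row of a two-row event. That row could then stay in the intensity tables as an additional entry for the same event. A programmer who guesses the intent departs from the written SAP.

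**Working it through.** **Inputs**
- Three grades: mild, moderate, severe (protocol 9.1.2).
- Each worsening adds one row, and the earlier row is closed and kept (protocol 9.1.2).
- Improvement requires no change of severity, so it is taken to add no row (protocol 9.1.2).
- SAP trigger: rows > 2 (SAP 7.7.3.3).
- Active group size: 6 per cohort (SAP 5.3).

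**Step 1: rows per event.** The recorded grades of one continuous event can only rise, so the number of rows equals the number of strictly increasing grades recorded. On three grades, the sequences with at least two rows number C(3,2) + C(3,3) = 3 + 1 = 4, and the longest has three rows. Enumerating all observed grade sequences up to length six, with improvement opening no row, gives the same four.

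| Path | Rows | Rows > 2 (as written) | Rows ≥ 2 (corrected) |
|---|---|---|---|
| mild → moderate | 2 | not covered | covered |
| moderate → severe | 2 | not covered | covered |
| mild → severe | 2 | not covered | covered |
| mild → moderate → severe | 3 | covered | covered |
| **Total covered** | | **1 of 4** | **4 of 4** |

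**Step 2: is there a rule elsewhere?**
- Protocol 10.4 says only "Adverse events will also be tabulated by severity and by relationship to study drug". It does not say which grade is used.
- SAP 7.7.3.3 has the sentence "The following calculations and derivations will be used, making the most conservative judgment", but what follows it are the derivations of study day and event duration, not severity.
- The entry for Table 14.3.1.3 repeats the layout of 14.3.1.2 and adds no maximum-intensity rule.

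**Step 3: effect on one table.** Take one subject with one mild-to-moderate worsening in a six-subject active group. Assume the mock tables give no maximum rule and both rows are tabulated.

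| Row of the table | As written | Two or more rows |
|---|---|---|
| Mild | 1/6 = 16.67% | 0/6 |
| Moderate | 1/6 = 16.67% | 1/6 = 16.67% |
| Preferred term, any grade | 1/6 = 16.67% | 1/6 = 16.67% |

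The threshold adds one lower-grade entry and changes nothing else.

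**Step 4: what the threshold does not cause.** Suppose a subject has two separate episodes of the same preferred term, one mild and one moderate. If no subject-level maximum is applied, the table shows mild 1/6 and moderate 1/6 under either wording. The threshold's contribution there is zero, so that overlap is a different question.

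**The case against.** The strongest reply is that the intent is obvious. The sentence is loosely drafted, its purpose is plainly to report a worsening event at its highest grade, and any experienced programmer would read it that way. The mock tables may say so outright. On two-row events the SAP is silent and does not order double counting, so the table in step 3 shows one possible handling. All of this stands, and it keeps the point minor. It does not make the written condition correct. If the mock tables do apply a maximum to two-row events, they and the SAP text need to agree.

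Three further objections have some force:
- **Improvement.** The protocol does not require a severity change on improvement, but it does not forbid a new row either. If a site re-records a fluctuating event, more than three rows are possible and the 1-of-4 ratio is no longer fixed. A single worsening still gives two rows.
- **Recording window.** Section 9.1.2 speaks of worsening during study drug administration. Applying it after a single injection needs that period to extend over follow-up. Section 9.2.2.2 defines it as running from drug initiation to end of study, but does so for serious adverse events.
- **Scale.** Protocol section 6.1.3 reports few adverse events and no serious ones among the 40 Part 1 subjects, so few events may be affected. The documents give no count of worsening events.

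None of these removes the two-row gap.

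**Conclusion.** The concern holds and is minor. As written, the highest-severity rule covers 1 of 4 possible worsening paths and 0 of 3 single-step worsenings. That is a statement about which cases the rule reaches, not how often they occur.

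The mismatch with protocol 9.1.2 is certain from the text. The effect on the tables is conditional on the mock tables not supplying the missing rule and on both rows being tabulated. In that case, each affected event adds one lower-grade entry in Table 14.3.1.3 and may do so in the intensity rows of Table 14.3.1.1. The subject's highest grade stays visible, the any-event and SOC/preferred-term subject counts are unchanged, the analysis is descriptive (SAP 7.1), and individual listings would show both rows.

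**What to change.** In SAP section 7.7.3.3, change the condition from more than two rows to two or more rows, and confirm that the mock tables and the programmed severity derivation agree. The cost is one phrase and that check; data collection does not change.

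Two related clarifications would help but are not needed to correct this error. One is whether each subject is counted once per SOC and preferred term at maximum intensity, which would settle the separate-episodes case. The other is how linked rows of one worsening event enter the event counts and the duration derivation, since the present rule sets only the severity.

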7.7.3.4 Safety Clinical Laboratory Evaluations

Laboratory parameters to be determined per protocol are:

Hematology	Chemistry	Urinalysis	Others
Hemoglobin	Creatinine and eGFR	Nitrates	FSH ^b
Hematocrit (packed cell volume [PCV])	Fasting glucose ^d	pH	Beta-HCG ^b
RBC count	Sodium	Glucose	
Platelet count	Potassium	Albumin or micro albumin	
WBC count	ALT	Erythrocytes	
Neutrophils	AST	Leukocytes	
Eosinophils	GGT	Ketones	
Monocytes	Bilirubin (total, direct and indirect)	Microscopy ^a	
Basophils	Alkaline phosphatase	Specific gravity	
Lymphocytes	Albumin	Creatinine	
Mean corpuscular volume	Cholesterol (total) – lipid status ^d	Protein	
Mean corpuscular hemoglobin ^f	LDL – lipid status ^d		
Mean corpuscular hemoglobin concentration ^f	HDL – lipid status ^d		
Erytoblasts ^f	Triglycerides – lipid status ^d		
Red blood cell distribution width (RDW-CV) ^f	LDH – lipid status ^d		
ESR	α-tocopherol ^e Rheumatoid factor ^c Chloride CRP hsCRP (Part 2 only) Calcium (corrected) Inorganic phosphate Uric acid Blood urea nitrogen Pancreatic lipase ^g		

^a If there is an abnormality in urine in accordance with the clinical laboratory standard procedures.

^b Required of postmenopausal females only during Screening.

^c Only at Screening.

^d Only at Screening, pre-dose on Day 1, Day 14 and Day 35 (Parts 1 and 2). For Part 3 at Screening and Day 169 (EOS).

^e Only pre-dose on Day 1, Day 14 and Day 35 (Parts 1 and 2). For Part 3 at Screening and Day 169 (EOS).

^f Only applicable for Part 2

^g Not on Day 92 of Part 3

Listings will be created of the laboratory data according to protocol and only present the original values, units and reference ranges as received from the laboratory.

All qualitative laboratory data will be supplied per lab manual, which is checked on the use of International System (SI) units by clinic and (if necessary) converted to SI units for the descriptive statistics.

Listings of all clinical laboratory data for each subject will be provided and values outside the normal range are flagged. For continuous data, abnormal values will be flagged with 'L' (low) for values below the lower limit of the laboratory's normal range, or 'H' (high) for values above the upper limit of the laboratory's normal range. Qualitative results outside of the laboratory's normal range will be flagged as 'A' (Abnormal). For evaluations (Normal, Abnormal NCS and Abnormal CS), the count and percentage will be provided.

Laboratory safety data will be summarized according to protocol scheme time point. Where applicable, change from baseline will also be calculated and summarized. Baseline is defined as the last value measured on Day -1 (or pre-dose on Day 1) The evaluations from baseline over time will be summarized as a shift table.

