General medical history	X	X ²⁴	X ²⁴												
Prior and concomitant medications	X	X	X	X	X	X	X	X	X	X	X	X	X		
Physical examination	X	X												X	
SOL-116 administration ⁶			X					X	X	X					
Injection site reactions			X ¹⁶	X	X			X ¹⁶	X ¹⁶	X ¹⁶					
12-lead ECG ⁷	X	X	X					X ¹⁷	X ¹⁷	X ¹⁷				X	
3-lead ECG (telemetry) ⁸			X												
Pregnancy testing ⁹	X	X						X	X	X				X	
Serology	X														
Serum FSH (postmenopausal women only)	X														
Blood sampling for SOL-116 PK			X ¹⁸	X	X	X	X	X ¹⁹	X ¹⁹	X ²⁰	X	X	X		
Blood sampling for immunogenicity			X ¹⁹					X ¹⁹	X ¹⁹	X ¹⁹		X ²¹	X		
Blood sampling for BSSL			X ¹⁸	X	X	X	X	X ¹⁹	X ¹⁹	X ²⁰	X	X	X		

Study Period	Screening	Treatment period										FU/EOS		
		Visit 1 ¹	Visit 2 ²			Visit 3	Visit 4 ³	Visits 5-6	Visit 7 (dosing day) ⁴	Visit 8 (dosing day) ⁴	Visit 9 (dosing day)	Visits 10-11	Visits 12-17	
Visit	Visit 1 ¹		Visit 2 ²			Visit 3	Visit 4 ³	Visits 5-6	Visit 7 (dosing day) ⁴	Visit 8 (dosing day) ⁴	Visit 9 (dosing day)	Visits 10-11	Visits 12-17	Visit 18
Assessments / Study days (visit windows in days)	Day -28 to Day -2	Day -1	Day 1	Day 2	Day 4 (72 hrs) (±1)	Day 8 (±1)	Days 11 and 15 (±1)	Day 29 (±1)	Day 57 (±3)	Day 85 (±3)	Day 86 and 88	Days 92, 95, 99, 113, 140, 154 (±3)	Day 169 (±5)	
Blood sampling for cytokine and chemokine panel			X ¹⁹		X	X		X ¹⁹	X ¹⁹	X ¹⁹	X ²²	X ²³	X	
Blood sampling for future exploratory analysis ¹⁰			X ¹⁹								X		X ¹⁵	X
Urine drugs of abuse and cotinine screen	X	X ¹⁹												
Alcohol test	X	X ¹⁹							X ¹⁹	X ¹⁹	X ¹⁹			
Serum biochemistry, lipid status, hematology, coagulation, urinalysis ¹¹	X	X ¹⁹			X	X		X ¹⁹	X ¹⁹	X ¹⁹	X ²²	X ¹⁵	X	
Baseline symptoms	X	X ²⁴	X ²⁴											
Ambulant visit	X				X	X	X	X	X	X	X	X	X	X
Residence in clinic ¹²		X	X	X										
AEs/SAEs reported/questions ¹³			X	X	X	X	X	X	X	X	X	X	X	X

Abbreviation: ADA, anti-drug antibodies; AEs, adverse events; BSSL, bile salt-stimulated lipase; CCP, cyclic citrullinated peptide; CRP, C-reactive protein; ECG, electrocardiogram; ESR, erythrocyte sedimentation rate; FSH, follicle stimulating hormone; PK, pharmacokinetics.

1. Screening can be divided over 2 visits.
2. Spare subjects not immediately included in the study may be kept in the clinic until it is decided whether these subjects are to be included. If subjects are included > 48 hours after admission in the clinic on Day -1, the Day -1 assessments have to be repeated.

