3. If the clinic visit is extended up to and including Day 6, Visit 4 will not take place. In that case, all assessments including blood sampling scheduled for Visit 4 will be performed on Day 6, at the discretion of the Investigator.
4. Study site should make a **phone follow-up with subject approximately 3 to 7 days after dose** to follow up adverse events and/or medication.
5. Not to be performed when this assessment was done within 3 weeks prior to dosing and result is available.
6. The PI must review Day -1 safety lab results prior to dosing.
7. Triplicate at Screening and on Day -1. On Day 1: 1 and 4 hours post-dose.
8. From 1 hour pre-dose until 6 hours post-dose.
9. Serum at Screening, urine at all other timepoints.
10. Only collected and analysed when the subject has given consent for the collection and future analysis of this sample in the informed consent form. Pre-dose on Day 1 and Days 85, 92 and 169.
11. Fasting glucose determined at Screening only. Lipid status determined only at Screening and Day 169 only (10 hours' fasting at both occasions). No pancreatic lipase on Day 92.

12. If medically indicated and/or based on emerging data, the clinic stay may be extended up to Day 7.
13. Starting from first study drug administration.
14. On Day 1: Prior to dosing and 1 and 4 hours post-dose. After the other doses: Prior to dosing and 4 hours post-dose.
15. Day 92 only
16. Assessed for four (4) hours after each injection and thereafter as needed.
17. Prior to dosing and 4 hours post-dose.
18. Pre-dose, 4 and 24 hours post-dose
19. Pre-dose only.
20. Pre-dose and 4 hours post dose.
21. Day 113 only.
22. Day 88 only
23. Days 92 and 113 only.
24. Up until first study drug administration.

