- d. Only at Screening.
- e. Only RA patients.
- f. Only at Screening, pre-dose on Day 1, Day 14 and Day 35 (Parts 1 and 2). For Part 3 at Screening and Day 169 (EOS).
- g. A SARS-CoV-2 rapid test will be performed on Day -1 (Part 1 only). At the discretion of the Investigator, a SARS-CoV-2 PCR or rapid test may be performed at other time points during the study.
- h. Only pre-dose on Day 1, Day 14 and Day 35 (Parts 1 and 2). For Part 3 at Screening and Day 169 (EOS).
- i. Only applicable for Part 2.
- j. Not on Day 92 of Part 3.

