8.11.2 Safety and Tolerability Parameters

Baseline is defined as the last value measured prior to SOL-116 administration (vital signs, ECG, laboratory parameters), unless otherwise specified.

The following parameters have been defined as parameters regarding safety and tolerability:

- Clinical laboratory evaluations;
- Injection site reactions;
- AEs;
- Immune reactions (e.g. hypersensitivity, cytokine release syndrome, immunogenicity);
- Vital signs;
- Physical examination;
- ECGs (3-lead telemetry and 12-lead ECGs);
- Concomitant medications/therapy.

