5.5 Study Flow Chart/Schedule of Events (SOE)

The study will consist of two parts.

In Part 1, there are a Screening period (Day -28 to Day -2), a treatment period (Day -1 to Day 63 ± 3), and a follow-up evaluation (Day 90 ± 3 days).

In Part 2, there are a Screening period (Day -28 to Day -2), a treatment period (Day -1 to Day 63 ± 3), and a follow-up evaluation (Day 90 ± 3 days).

In Part 3, there are a Screening period (Day -28 to Day -2), a treatment period (Day -1 to Day 154 ± 3), and a follow-up evaluation (Day 169 ± 5 days).

The complete schedules of prescheduled visits and all procedures for Part 1, Part 2, and Part 3 are presented in Table 5-1, Table 5-2, and Table 5-3 respectively in the CSP.

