7 REPORT SPECIFICATIONS AND STATISTICAL ANALYSES

7.1 General Considerations

For safety and tolerability analyses, the descriptive statistics presented will be frequency counts (n) and percentages for qualitative variables. Quantitative variables will be summarized using the number of available observations (n), mean, median, standard deviation (SD), minimum (min), and maximum (max) values.

For decimal display, appropriate rounding will be performed for all summary table: mean and median will be presented with one more decimal than the original data; SD will be presented with two more decimals than the original data; minimum and maximum values will be presented with the same precision as the original data. Percentages will be presented with 2 decimals and no decimals will be presented for integer value (For example, zero will be presented as 0 %).

Extra measurements (such as additional visits or repeat assessments) will not be included in the descriptive statistics but will be included in subject listings only.

For the calculation of baseline corrected values, baseline is defined the last value measured prior to (the first) study drug intake (vital signs, ECG, laboratory parameters, bile salt-stimulated lipase, C-reactive protein (CRP), erythrocyte sedimentation rate (ESR), and S-calprotectin and high sensitive CRP (hsCRP) (only RA patients)), unless otherwise specified. If no value prior to dosing is collected, the baseline value will be treated as missing for analysis.

For any results reported as above upper limit of quantification (>ULOQ), the numeric value for calculating summary statistics used to replace this label will be the ULOQ value, plus one unit of the smallest digit of the ULOQ number. For example, if the ULOQ is 2.3 units then the smallest digit is 0.3 and one unit greater at that decimal point would be 0.4. A ULOQ designation would then be replaced numerically as 2.3 + 0.1 or 2.4 units. Similarly, if the ULOQ was 20.3, then ">ULOQ" would be replaced by 20.4. In addition, for any results reported as below lower limit of quantification (<LLOQ), the numeric value used for this label will be the half of LLOQ value. For

example, if the LLOQ is 0.5 units then the final value for statistical summary will be the half of 0.5 which is a value 0.25 units. In case an >ULOQ or <LLOQ value will be replaced as described here (for the purpose of summarizing the data), this will be indicated in a footnote beneath the table.

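### The laboratory section of the SAP restricts baseline to Day -1 or pre-dose Day 1; read literally, Part 3 lipids and alpha-tocopherol have no baseline and so no change or shift summary

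*SAP*

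**What the plan says.** Three places define a laboratory baseline.

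- SAP 7.7.3.4: "Baseline is defined as the last value measured on Day -1 (or pre-dose on Day 1". The next sentence builds on it: "The evaluations from baseline over time will be summarized as a shift table".
- SAP 7.1, which names laboratory parameters among the variables covered: "baseline is defined the last value measured prior to (the first) study drug intake". It allows exceptions specified elsewhere, and it treats baseline as missing when no pre-dose value was collected.
- Protocol 8.11.2: "Baseline is defined as the last value measured prior to SOL-116 administration (vital signs, ECG, laboratory parameters), unless otherwise specified".

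The Part 3 schedule is as follows.

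- SAP 5.5: "In Part 3, there are a Screening period (Day -28 to Day -2".
- Protocol Table 5-3 marks the row "Serum biochemistry, lipid status, hematology, coagulation, urinalysis" at Day -1, but its footnote 11 says "Lipid status determined only at Screening and Day 169 only". Protocol 8.3.4.11 agrees.
- Protocol Table 8-1, footnotes f (lipid status, with LDH printed under that label) and h (alpha-tocopherol): "For Part 3 at Screening and Day 169 (EOS". SAP 7.7.3.4, footnotes d and e, repeats this.

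SAP 10.2 plans change from baseline for serum biochemistry in table 14.3.5.2 and shifts in table 14.3.5.5. SAP section 8 declares no significant change from the protocol's analyses.

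**The concern.** A Screening sample taken between Day -28 and Day -2 can never satisfy a rule that accepts only Day -1 or pre-dose Day 1. Any Part 3 test whose sole pre-dose sample is at Screening therefore loses its baseline under 7.7.3.4 and keeps it under 7.1 and the protocol. The text does not settle which rule governs, so two programmers could produce different tables from the same data.

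Laboratory evaluations belong to the primary endpoint in every part (protocol 8.1.1), and Part 3 is the only part with repeated dosing. These tests have one value before dosing and one after. Change and shift are the planned summaries that compare the two within a subject.

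**Working it through.** **Check of the schedule against the plan's own counts (Part 3, Table 8-5)**

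- Alpha-tocopherol: Screening + Day 169 = 2 draws, and 2 × 6.0 mL = 12.0 mL, as printed. No draw is left for Day -1 or Day 1.
- Haematology and coagulation: Screening and Days -1, 4, 8, 29, 57, 85, 88, 92 and 169 = 10 draws, as printed.
- Total volume: 49.5 + 3.5 + 30.0 + 27.0 + 80.0 + 21.0 + 40.0 + 4.0 + 20.0 + 3.5 + 12.0 + 22.0 = 312.5 mL, as printed.

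**Applying each baseline rule to the sampling days**

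| Tests | Pre-dose samples | Baseline under SAP 7.7.3.4 | Baseline under SAP 7.1 / protocol 8.11.2 |
|---|---|---|---|
| Part 3 lipid status | Screening | none | Screening |
| Part 3 alpha-tocopherol | Screening | none | Screening |
| Other Part 3 chemistry and haematology drawn at Day -1 | Screening, Day -1 | Day -1 | Day -1 |
| Parts 1 and 2 lipid status | Screening, Day 1 pre-dose | Day 1 | Day 1 |
| Parts 1 and 2 alpha-tocopherol | Day 1 pre-dose | Day 1 | Day 1 |

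The two rules part only for Part 3 tests sampled at Screening and Day 169. Parts 1 and 2 are unaffected as long as the Day 1 pre-dose sample exists. SAP 7.2 rules out imputation, so nothing fills the gap.

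**Size**

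- Tests affected: total cholesterol, LDL, HDL, triglycerides and alpha-tocopherol = 5; with LDH, 6.
- Share of the 25 chemistry rows in the SAP laboratory table: 5/25 = 20%; 6/25 = 24%.
- Subject-by-test changes possible in MD1 (8 subjects): 5 × 8 = 40; 6 × 8 = 48. Summarized under 7.7.3.4: 0.
- With MD2 on the same schedule (16 subjects): 5 × 16 = 80; 6 × 16 = 96. Summarized under 7.7.3.4: 0.
- Under SAP 7.1 all of these are summarized if both samples are collected. Since Day -1 is one day before dosing, the Screening baseline is 2 to 28 days old at first dose.

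**The case against.** The strongest reply is that the wide rule may already govern. SAP 7.1 makes a baseline missing only when no pre-dose value was collected, and in Part 3 one is collected. On that reading 7.7.3.4 merely names the days on which the last pre-dose sample usually falls, and protocol 8.11.2 and SAP section 8 support it. This shows that the loss is conditional. It does not show that the text is sound: 7.1 and 8.11.2 both give way to a more specific definition, and 7.7.3.4 is the only definition in the SAP written specifically for laboratory data. The SAP's limit of the change summary to applicable tests does not help either. It attaches to the change sentence, not to the shift table, and it would simply tell the programmer to leave the rows out.

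Three smaller points deserve an answer.

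- **The extra chemistry draw.** Table 8-5 counts 11 Part 3 chemistry draws (4.5 mL × 11) against 10 on the schedule. In Parts 1 and 2 the same one-draw excess (12 against 11) fits the pre-dose Day 1 glucose and lipid sample. The Part 3 draw is assigned to no day, and the footnotes expressly confine lipids to Screening and Day 169. Even if it were a Day 1 lipid sample, alpha-tocopherol, which has its own row, would still have no baseline.
- **The denominator.** The 25 rows include hsCRP, which applies to Part 2 only. On 24 rows the shares are 5/24 = 20.8% and 6/24 = 25%. The picture does not change.
- **Unseen table shells.** The mock tables are separate documents and might show a missing-baseline category. That would display the gap, not close it.

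The objection that the practical effect is small stands, and it sets the rating.

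**Conclusion.** The concern holds, as a minor point. SAP 7.7.3.4 is narrower than SAP 7.1 and protocol 8.11.2. Applied as written, it empties the Part 3 change and shift rows for five chemistry tests, or six with LDH, for every subject.

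This rests on three assumptions: the laboratory-specific sentence is the one programmed, the footnoted Part 3 schedule is followed, and MD2, if run, keeps that schedule.

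The data themselves are not lost. Absolute values are summarized by group at both time points, individual values are listed and flagged, and each change can be derived from the listings. No inference is planned, and no decision rule in the documents depends on these changes.

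**What to change.** Replace the baseline sentence in SAP 7.7.3.4 with: *Laboratory baseline is the last non-missing value before the first dose of study drug, Screening included (see Section 7.1).* Wherever a Day -1 or pre-dose Day 1 value exists, the baseline is unchanged. A narrower wording would also work: keep the present rule and name Screening as baseline for Part 3 tests not sampled on Day -1 or Day 1. The general wording is preferable because it leaves a single definition across the SAP and protocol.

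The cost is one sentence, with no new sample, visit or data. SAP 3.1 locks and unblinds part by part, so the edit should be in place before the Part 3 lock. If Part 3 is already locked, record the change in the clinical study report.

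A separate text correction is also needed. Part 3 fasting glucose is at Screening only in protocol 8.3.4.11 and Table 5-3 footnote 11, but at Screening and Day 169 in Table 8-1 footnote f and SAP footnote d. These passages must be reconciled. If glucose is drawn on Day 169, it is one more test affected by the baseline rule.
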